mindfulness (13, 14), stress symptoms (14, 15), emotion regulation (16), and quality of life and general health (15, 17) in Western and Asian countries. However, no study has examined the effectiveness of mindfulness-based interventions among ESRD patients undergoing hemodialysis in the Arab countries such as Kuwait. Therefore, any generalization of these previous study findings to other hemodialysis patients of different cultures such as ESRD patients in Kuwait is limited due to the different belief systems and self-care practices of these cultures. Thus, the current study aimed to examine the effects of a mindfulness-based intervention on trait mindfulness, perceived stress, emotion regulation, and health-related quality of life in ESRD patients undergoing hemodialysis in Kuwait.

Theoretically, investigating the effects of mindfulness meditation on the selected variables may provide insight into the mechanisms through which mindfulness meditation impacts quality of life in hemodialysis patients. The current study findings may enrich the body of knowledge on mindfulness meditation and bridge the gap in the literature regarding the effects of mindfulness meditation on patients receiving hemodialysis. Practically, the findings of the present study may guide decision-makers in adopting mindfulness meditation in Kuwaiti hospitals.

Methods

Design

This study used a repeated-measures, randomized, wait-list, control design and was conducted between January 2021 and May 2021 in the dialysis center at Jahra Hospital, Kuwait. Seventy-four ESRD patients undergoing hemodialysis were recruited using convenience sampling. Jahra Hospital is a governmental hospital with one of the biggest dialysis centers in Kuwait, with a female ward, male ward, and isolation ward. The center holds 70 dialysis machines/beds, with an average number of 30 patients managed per day.

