2. Being mindful of the body, which includes attending to how the body feels from head to toes and noticing any sensations that come and go. Upon noticing a sensation, the individual must gently note it, let it go, and continue attending to how the body feels (5 minutes).
3. Being mindful of thought, which includes attending to the mind as thoughts come and go. Whenever a thought or feeling comes to mind, the individual should just notice it, let it go, and continue attending to the mind repeatedly (5 minutes).
4. Being mindful of sounds, which includes attending to the sounds one hears, without thinking about them. The individual must gently notice the sound, let it go, and continue waiting (5 minutes).
5. Being mindful of taste, which includes imagining a wonderful bowl of pieces of one's favorite fruit and simply attending to a taste sensation, without thought, analysis, or effort (5 minutes)
6. Full meditation, which includes gently opening one's eyes and being mindful of the world of the moment, quietly attending, and waiting. When noticing something, be it a sight, sound, thought, or sensation, the individual must let it go and then resume attending, doing nothing else, and waiting for what comes next (5 minutes).

The experimental group received 30-minute individually administered, guided, chairside interventions during their hemodialysis sessions. This protocol has been found to

be feasible and effective for patients undergoing hemodialysis (6). Smith (2005) explained in his ABC relaxation theory that at least two and preferably five weekly 30-minute sessions of actual training of mind-body therapies should be provided to evoke relaxation, relieve stress, and improve health in general populations. However, for hemodialysis patients, it has been suggested that brief program formatting with at least 400 total minutes may lead to greater health benefits (18). Accordingly, the experimental group received 30-minute mindfulness meditation sessions 3 times a week for 5 weeks (450 minutes)

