The participants also received a 2-hour foundation course which was introduced and supervised by one of the study researchers prior to the actual training sessions and which taught the participants the intervention basics, benefits, protocol, and method of access. To ensure the consistent delivery of the intervention, the researcher recorded the intervention instructions in Arabic based on the Smith (2005) protocol and sent the audio-recorded instructions to the participants via WhatsApp or email. The audio-recorded intervention contents were validated by 2 psychologists and experts in meditation. The recorded intervention instructions were accessed by the participants during the sessions using their cell phones and headsets, as recommended (18). This method allowed for up to 3-5 participants to listen to the instructions and perform the intervention simultaneously.

The researcher who was responsible for developing the study intervention and supervising the intervention delivery was an experienced mind-body practitioner who had received a 4-day training course on mindfulness meditation. The researcher attended the sessions to manage any potential interruptions and evaluate the intervention delivery. The participants' privacy was maintained using curtains surrounding each participant during the intervention. The participants were asked not to share any information related to the intervention with the participants in the control group.

The participants in the control group were instructed to sit with their eyes closed and relaxed for 30 minutes 3 times a week for 5 weeks during hemodialysis sessions to control for the nonspecific effects of social interaction and environment (35). The timings of the control group sessions were similar to those of the experimental group, whereby if a given experimental group intervention lasted for 30 minutes, the control group participants would be asked to sit with their eyes closed and relax for 30 minutes also.

Procedure

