First, the permission from the instruments used in the study was obtained. Recruitment of participants was conducted by one of the study researchers after obtaining approval to conduct the study from the hospital administrators. The study purposes and protocol were explained to the patients in detail. Patients who agreed to participate in the study and met the eligibility criteria were asked to sign a consent form, and the participating patients were then randomly assigned to the two study groups. The baseline measurements of the study variables were taken using the self-report questionnaires, which were administered by a research assistant who was not involved in any other parts of the study. The study variables were also measured two weeks post the start of the intervention and at the end of the final session for both groups under the same conditions. All measurements were privately taken at the dialysis center.

Data Analysis

SPSS version 25 (SPSS Inc., Chicago, Illinois, USA) was used to analyze the collected data. Prior to the main analysis, outliers and missing data were examined and managed as appropriate. Then, the assumptions of the statistical tests used, normality using histogram graph, homogeneity of variance, and sphericity were checked and managed as appropriate. Mauchly's test of sphericity is used to assess whether the sphericity assumption has been violated. When Mauchly's test of sphericity was significant ($p < .05$),

the degrees of freedom were corrected using Greenhouse-Geisser estimates of sphericity. The comparability of the two groups was evaluated in terms of demographic characteristics and the baseline measurements of the dependent variables using t-test and Chi square, based on the measurements of the dependent variables. The main analysis was conducted with repeated-measures ANOVA (mixed design: within and between groups). A P-value of 0.0125 was set as the significance level for the main analysis tests. The p-value was adjusted due to multiple testing by dividing the p-value of .05 by 4 (number of dependent variables).

Ethical Considerations

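### The main analysis names no effect, contrast or endpoint visit, so a significant three-visit ANOVA does not establish a between-arm difference at the end of the programme

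*Combined protocol and SAP*

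**What the plan says.** Each outcome is measured three times. The Procedure section gives a baseline ("The baseline measurements of the study variables were taken using the self-report questionnaires") and two later visits: "The study variables were also measured two weeks post the start of the intervention and at the end of the final session for both groups".

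In the Intervention section, "the experimental group received 30-minute mindfulness meditation sessions 3 times a week for 5 weeks (450 minutes". The reason offered for that length is that "it has been suggested that brief program formatting with at least 400 total minutes may lead to greater health benefits". A preparatory course precedes the sessions ("The participants also received a 2-hour foundation course") and is not counted in the 450 minutes.

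Under Data Analysis, "The main analysis was conducted with repeated-measures ANOVA (mixed design: within and between groups", and "A P-value of 0.0125 was set as the significance level for the main analysis tests". The section does not say whether the interaction or the group effect is to be read. It names no planned contrast or follow-up comparison, and it does not say which visit carries the conclusion. Determination of the Sample Size gives 56 subjects for power 0.95, effect size 0.25 and alpha 0.0125.

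**The concern.** A three-level group-by-time test asks whether the difference between arms changes anywhere across baseline, week 2 and the end. It does not ask whether the arms differ once the programme is complete. Week 2 falls 180 scheduled minutes into a 450-minute programme, short of the 400 minutes that the plan cites when choosing the length. A difference seen at that visit and gone by the end can make the main test significant, and the plan specifies no further test to show which visit produced the result. A statement that the five-week programme works would then rest on a test that does not address it. A test aimed at the end of the programme can also be more powerful with the same data.

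**Working it through.** **Inputs.** From the documents: three visits; 37 per arm (Design); alpha 0.05/4 = 0.0125; f = 0.25, power 0.95, N = 56 (Determination of the Sample Size); 30 minutes, 3 times a week, 5 weeks (Intervention). Assumed because not given: correlation between visits ρ = 0.5 (range 0.3 to 0.7), equal SDs, sphericity, complete data.

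**1. The plan's own figure.** For a within-between interaction with k = 2 arms and m = 3 visits, λ = f²·N·m/(1−ρ), df1 = (k−1)(m−1) = 2 and df2 = (N−k)(m−1).
- N = 56: λ = 0.0625 × 56 × 3/0.5 = 21.0, df 2 and 108, power 0.952.
- N = 54: power 0.943. So 56 is the smallest even N that reaches 0.95.
- With m = 2 the same inputs need 72. The between-group effect with m = 3 needs 188.
- The within-subject time effect with m = 3 also gives 56, but it does not compare the arms.

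The stated size therefore fits the three-level interaction, with week 2 counted as a full level.

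**2. Scheduled exposure at week 2.** 2 × 3 × 30 = 180 minutes; 180/450 = 40% of the programme and 180/400 = 45% of the cited figure.

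**3. What the interaction responds to.** For between-arm differences d (in SD) at the three visits, with mean d̄ and n per arm, λ = (n/2)·Σ(d−d̄)²/(1−ρ). With n = 37, df are 2 and 144.
- Week 2 only, 0.5 SD: Σ(d−d̄)² = 0.25 × 2/3 = 0.1667; λ = 18.5 × 0.1667/0.5 = 6.17; power 0.373.
- Week 2 only, 0.7 SD: λ = 18.5 × 0.49 × (2/3)/0.5 = 12.09; power 0.733.
- Over ρ = 0.3 to 0.7 these become 0.25 to 0.64 and 0.54 to 0.95.
- A difference of 0.75 SD at week 2 only has power 0.806. The same difference at the end only also has 0.806, because λ is unchanged when the visits swap places.
- If the group main effect were read instead, it too weights the two visits equally: 0.113 for either pattern at 0.75 SD.

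In the week-2-only case, a comparison of the arms at the end, with or without baseline adjustment, rejects at its nominal 0.0125.

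**4. Power for a true end-of-programme difference of 0.5 SD (n = 37, ρ = 0.5).**

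| Test | Effect at week 2 | Power |
|---|---|---|
| Three-visit interaction | 40% of final: λ = 18.5 × 0.1267/0.5 = 4.69 | 0.27 |
| Three-visit interaction | full, or nil: λ = 6.17 | 0.37 |
| Change from baseline to end | any | 0.35 |
| End score adjusted for baseline | any | 0.47 |

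For the last row the residual SD is √(1−ρ²) = √0.75, so the noncentrality is 0.5/√(0.75 × 2/37) = 2.48 on 71 df. At ρ = 0.3 the adjusted test has 0.39 against 0.17 to 0.25 for the interaction. At ρ = 0.7 it has 0.67 against 0.49 to 0.64.

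**5. What f = 0.25 means as a difference.** If the arms differ by d at one post-baseline visit only, f = (d/2)·√(2/9). Setting f = 0.25 gives d = 1.06 SD. At N = 56 (28 per arm) and ρ = 0.5, the baseline-adjusted end comparison has power 0.974 for that difference.

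**The case against.** **Measuring mid-programme is ordinary practice.** This stands. A repeated-measures design measures before, during and after, and a randomised difference at week 2 would be a real early effect, not a false positive. Nor do the documents say that such a difference would be reported as benefit of the full programme. The gap is the unnamed endpoint, not the visit.

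**A reader might infer that 400 minutes are required and that week 2 is too early to show benefit.** The documents do not support this. The wording is a suggestion of greater benefit and sets no threshold. The 180 minutes is also only scheduled exposure: it assumes full attendance, although the plan anticipates 30% non-attendance, and it leaves out the two-hour course. The argument about the test does not depend on the 400-minute figure.

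**A reader might infer that a mediation analysis is owed.** The Introduction says only that the work "may provide insight into the mechanisms through which mindfulness meditation impacts quality of life in hemodialysis patients". That is a hope attached to the study's significance. The stated aim is the effect on four outcomes, so such an analysis is optional.

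**The fading pattern is extreme, and power matters little at the planned effect.** Nothing in the documents predicts a difference that vanishes while sessions continue, and the theory in the Introduction points towards growth. At 1.06 SD, 37 per arm and ρ = 0.5, the interaction has power 0.955 under the 40% pattern and the unadjusted baseline-to-end contrast 0.975, so the choice barely matters there. Both points are fair. The fading case shows what the test cannot distinguish; it is not a forecast. The power gain matters for differences well below 1.06 SD.

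**The change affects the sample-size section.** This also stands: 56 relies on three levels, so its basis must be rewritten.

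**Conclusion.** The concern holds in this form: as written, the main analysis cannot by itself support a conclusion about the completed programme. At 37 per arm and alpha 0.0125, a difference confined to week 2 is declared significant with probability 0.37 (0.5 SD) or 0.73 (0.7 SD), the same as for an equal difference confined to the end. The ranges in the working show how far this depends on the visit correlation, which the plan does not give. The figures also assume equal SDs, sphericity and no dropout; fewer completers would lower them (0.75 SD at week 2 only: 0.806 with 74 patients, 0.648 with 56).

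That the interaction is the intended test is an inference. It rests on the reproduction of 56, but the group effect would weight the visits equally too. The result does not show that 56 is wrong for the test it was computed for.

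**What to change.** For each of the four outcomes, state that the main test is the between-arm difference at the end of the final session, adjusted for the baseline score, at alpha 0.0125. Use ANCOVA, or the corresponding contrast in a longitudinal model with both post-baseline visits. Name week 2 as a secondary, early-response time point on which no claim about the full programme rests.

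Restate the sample-size basis for that contrast, giving the difference in SD units and the assumed correlation. By the normal approximation, 1.06 SD at ρ = 0.5 needs 2 × 0.75 × (2.498 + 1.645)²/1.06² ≈ 23 per arm for power 0.95, before dropout. At 0.5 SD, 37 per arm gives 0.47.

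The cost is a few sentences under Data Analysis and a rewritten sample-size paragraph. No new data are needed. With baseline adjustment, power exceeded that of the interaction in every pattern checked; an unadjusted change score would lose slightly (0.35 against 0.37) if the week-2 effect were full or nil.

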The inclusion criteria for participation in this study were being a patient with ESRD undergoing hemodialysis three times a week, being aged 18 years old or over, and being able to read and write in Arabic. The exclusion criteria included being a patient with cognitive dysfunction or mental retardation, taking psychopharmacological drugs, or undergoing psychotherapy. A research assistant, who was not involved in the recruitment or patient assessment processes, randomly assigned the participants to the intervention group (n=37) or the control group (n=37) using a simple 1:1 computer-generated sequence. The trial is reported in accordance with the CONSORT guideline.

Determination of the Sample Size

The required sample size was calculated using G-power version (3.1). Given a mixed-design (within groups and between groups) repeated measures ANOVA, power of 0.95, moderate effect size of 0.25, and α of .0125, the required sample size was 56 subjects. A P-value of 0.0125 was set as the significance level for the main analysis tests. The p-value was adjusted due to multiple testing by dividing the p-value of .05 by 4 (number of dependent variables). In a similar study, an attrition rate of 30% and a non-attendance rate of 30% (excluding dropouts) were estimated (18). Thus, taking into consideration of 60% attrition and nonattendance rates, the final total sample size was 89 patients.

Data Collection Instruments

The study data were collected using an Arabic self-report questionnaire with five parts:

Demographic characteristics. This section included a question for each following variable: Age, gender, employment status, nationality, family status, and educational levels.

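### The final assessment is tied to the last session with no week or window, so patients who stop or miss that session have no clearly defined final measurement

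*Combined protocol and SAP*

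**What the plan says.** - **Procedure.** After a baseline measurement: "The study variables were also measured two weeks post the start of the intervention and at the end of the final session for both groups". The same sentence adds that conditions were alike in the two groups, and the next one places all measurements at the dialysis centre.
- **Intervention.** The meditation arm has three 30-minute sessions a week for five weeks, which is 15 sessions or 450 minutes. The control arm rests with eyes closed on the same schedule. Both take place during dialysis.
- **Design, eligibility.** Patients must be "undergoing hemodialysis three times a week".
- **Determination of the Sample Size.** Citing a similar study, "an attrition rate of 30% and a non-attendance rate of 30% (excluding dropouts) were estimated". The plan then adds the two rates: "taking into consideration of 60% attrition and nonattendance rates, the final total sample size was 89 patients".
- **Data Analysis.** The main analysis is a mixed-design repeated-measures ANOVA in SPSS. On missing data the section says only that they were looked at and suitably handled.

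The document contains no intention-to-treat statement, no definition of an analysis population, no distinction between stopping the sessions and leaving the study, and no rule for assessing a patient who has stopped.

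**The concern.** The middle assessment can be dated for any patient from the start of the intervention. The last one can be dated only through a session. For a patient who stops at, say, session 7, the final session may mean the scheduled fifteenth, which gives an assessment at about week 5. It may also mean the patient's own last session, which gives an assessment close to the week-2 one, or none at all. The plan does not say which applies.

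Whether a final outcome exists, and when it is taken, can then depend on adherence after randomisation. The two arms ask different things of the patient (a guided programme against quiet rest), so adherence need not be equal. If patients without a final measurement are left out, randomisation no longer protects the comparison, which becomes meditation completers against rest completers. The plan itself expects losses large enough for this to matter.

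**Working it through.** **Inputs from the documents.** Three time points and two groups; "power of 0.95, moderate effect size of 0.25"; alpha 0.05/4 = 0.0125; required N 56; final N 89; 74 recruited and split 37/37; 30% attrition and 30% non-attendance excluding dropouts.

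**Assumed, not stated.** Correlation between repeated measurements rho = 0.5 (also 0.3 and 0.7) and sphericity (epsilon = 1).

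**Step 1: reproduce the plan's figures.** For the group-by-time interaction, lambda = f² × N × m/(1 − rho), df1 = (k − 1)(m − 1), df2 = (N − k)(m − 1), with k = 2 and m = 3.
- At N = 56: lambda = 0.0625 × 56 × 3/0.5 = 21.0, df = 2 and 108, power 0.952.
- At N = 54: power 0.943. So 56 is reproduced.
- Inflation: 56 × 1.6 = 89.6, given as 89. The second 30%, for non-attenders, is therefore part of the sample-size allowance.

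**Step 2: who has a defined final measurement?**

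| Patient | Final measurement under the current wording |
|---|---|
| Attends all sessions | Defined, nominal week 5 |
| Misses some, attends the last | Defined, nominal week 5 |
| Misses the last session | Not clearly defined |
| Stops early, still dialyses at the centre | Not clearly defined |
| Withdraws consent or leaves the centre | None, under any wording |

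The third and fourth rows are the gap.

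**Step 3: conditional illustration of numbers.**
- After 30% attrition: 74 × 0.70 = 51.8, about 52.
- If every non-attender also lacks a final measurement: 74 × 0.70 × 0.70 = 36.3, about 36 (49%).

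**Step 4: power if only those patients are analysed** (f = 0.25, alpha 0.0125, numbers rounded down).

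| Analysed | rho 0.3 | rho 0.5 | rho 0.7 |
|---|---|---|---|
| 74 | 0.941 | 0.991 | 1.000 |
| 51 | 0.791 | 0.927 | 0.996 |
| 36 | 0.586 | 0.774 | 0.961 |

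The target is 0.95.

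**Step 5: two hypothetical figures.**
- *Precision.* If every non-attender were lost under the current wording and every one recovered under a calendar rule, the ratio of standard errors would be sqrt(0.70/0.49) = 1.195, about 20%. The documents establish neither condition.
- *Bias with no true effect.* Bias = r × [phi(z1)/p1 − phi(z2)/p2], where p1 and p2 are the completion rates in the two arms, z1 and z2 the matching normal quantiles, and r the correlation between completing and improving. The ratio phi(z)/p is 0.497 at 70%, 0.195 at 90% and 0.644 at 60%. For 70% against 90%, 0.302 × r with r = 0.2 to 0.5 gives 0.06 to 0.15 SD. For 60% against 90%, 0.449 × r gives 0.09 to 0.22 SD. With the lower completion in the meditation arm the bias favours meditation; with the rates swapped it has the same size and the opposite sign; with equal rates it is zero. No input here comes from the documents.

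**The case against.** The strongest reply is that the final session is a scheduled time point. Both arms follow the same five-week schedule, control sessions are timed like the meditation sessions, and conditions of measurement are the same. On that reading the assessment falls at about week 5, and a patient who has stopped could still be assessed on the day the fifteenth session is due. This is a natural reading and much of it stands. It remains an inference, however: the Procedure gives no week, and it does not say that patients absent from the session are still approached.

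Three further objections stand:
- A reader might infer that anyone who misses sessions has no final measurement. That is too broad, because attending the last session is enough.
- A reader might infer that the plan excludes these patients. No sentence does so. Exclusion follows from the usual behaviour of a repeated-measures ANOVA combined with an unspecified missing-data method. That is partly a matter of the analysis and not only of visit timing.
- Non-attendance is not defined, so equating it with having no final measurement is an assumption.

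It is also fair that entry on thrice-weekly dialysis does not guarantee continued presence or cooperation, and that patients may withdraw at any time.

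**Conclusion.** The point holds as a gap in the timing rule, and a cheap improvement is available. The last assessment has no week or window, and for patients who stop or miss the last session it is not clearly defined. Enlarging the sample for non-attenders as well as dropouts suggests, without stating it, that neither group was expected to supply analysable data. With a standard repeated-measures ANOVA and no stated analysis by randomised arm, they would probably be excluded.

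The reduction from about 52 to about 36 of the 74 patients is conditional on every non-attender lacking a final measurement; it is not a forecast. The power figures rest in addition on the assumed rho. A reader might infer that the result is biased in favour of meditation, or that standard errors rise by about 20%. The documents support neither: they give one overall rate with no split by arm, and greater loss in the rest arm would reverse the sign. The size and direction of any bias are unknown.

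**What to change.** In the Procedure, replace the session-based timing of the last measurement with a calendar rule that is the same in both arms. Suggested wording: at the dialysis visit 5 weeks (with a stated window, e.g. ± 3 days) after the patient's first scheduled session, in every randomised patient who has not withdrawn consent to data collection, whatever the number of sessions attended.

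Add two statements: that stopping the sessions is distinct from withdrawing from the study, and that patients are analysed in the arm to which they were randomised.

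**Cost.** A few sentences. No extra visits should be needed for patients who still dialyse at the centre, since measurements are already taken there. Including non-attenders may make the estimated effect somewhat smaller, but it is then the effect in the groups as randomised. Patients who withdraw consent or leave the centre are still not recovered, so the missing-data method needs to be specified as well.

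### The main repeated-measures ANOVA appears to treat baseline as one of three outcome levels and names no treatment test; a baseline-adjusted model of the two later visits would usually be more efficient.

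*Combined protocol and SAP*

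**What the plan says.** Under Procedure, each outcome is taken at baseline and then "measured two weeks post the start of the intervention and at the end of the final session", which makes three occasions. Data Analysis gives the model in one sentence: "The main analysis was conducted with repeated-measures ANOVA (mixed design: within and between groups". It names no covariate, does not list the levels of the time factor, and does not say whether the group effect or the group-by-time interaction is the treatment test. Apart from that model, the only stated use of baseline is a comparability check on demographics and "the baseline measurements of the dependent variables using t-test and Chi square". The same section provides for Mauchly's test with a Greenhouse-Geisser correction, and sets 0.0125 per outcome.

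The sample size rests on the same model: "Given a mixed-design (within groups and between groups) repeated measures ANOVA, power of 0.95, moderate effect size of 0.25", with alpha 0.0125 and a result of 56. The number of measurements and their correlation are not stated.

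Two passages bear on when baseline was taken. Procedure puts it after allocation in the narrative: "the participating patients were then randomly assigned to the two study groups. The baseline measurements of the study variables were taken". Intervention describes "a 2-hour foundation course which was introduced and supervised by one of the study researchers prior to the actual training sessions".

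**The concern.** When baseline is an outcome level, the interaction test compares the arms on change. Change subtracts the whole baseline score, whereas regression subtracts only the part that predicts follow-up, so change carries extra noise unless the correlation is close to 1. The unnamed treatment test compounds this. A reader of the output could take the between-group F as the result, and that F dilutes any effect by averaging in a visit at which there can be none. What is at stake is power and clarity about the primary test in a modest trial: "Seventy-four ESRD patients undergoing hemodialysis were recruited using convenience sampling", against an inflated target of 89.

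**Working it through.** **Inputs.** From the plan: f = 0.25, alpha 0.0125, power 0.95, N = 56, two equal arms, three occasions. Assumed: equal variances, one common correlation r between occasions, and r from 0.3 to 0.85. The documents give no r for dialysis patients. The nearest figure is the test-retest reliability of .85 cited for the Perceived Stress Scale, a scale described as validated in college students; no interval is stated.

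**Reproducing 56.** For the interaction with m measurements, the noncentrality is f² × N × m / (1 − r), with (m − 1) and (N − 2)(m − 1) degrees of freedom. With m = 3 and r = 0.5: 0.0625 × 56 × 3 / 0.5 = 21 on 2 and 108 df, power 0.952. The figure of 56 reproduces. At r = 0.3 the requirement is 78 and at r = 0.7 it is 36.

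This does not prove three levels. Two measurements at r = 0.62, or four at r = 0.39 to 0.40, also give 56, and so does the test of time. Better support is the sphericity step, which has content only with three or more levels; since only three occasions exist, baseline would have to be one of them. That step may be standard wording, so the reading remains an inference.

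**Between-group F.** Its noncentrality is f² × N × m / (1 + (m − 1)r). At N = 56, m = 3, r = 0.5 this is 10.5 / 2 = 5.25, power 0.39. Reaching 0.95 needs 96 (r = 0), 150 (0.3), 188 (0.5) or 224 (0.7). It is not the test behind 56.

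**Variance of the end-of-treatment contrast** (outcome variance 1). Change from baseline: 2(1 − r). Baseline-adjusted: 1 − r². The ratio is (1 + r)/2, that is 0.65, 0.75, 0.85 and 0.925 at r = 0.3, 0.5, 0.7 and 0.85.

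**Power at N = 56, alpha 0.0125** (simulated). The adjusted test is the joint group effect over both later visits, on 2 and N − 4 = 52 df. Linear means half the end effect at week 2, plateau the full effect at both visits, late the effect at the end only.

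| r | End effect | Pattern | Interaction | Joint adjusted |
|---|---|---|---|---|
| 0.5 | 1.22 SD (f = 0.25) | linear | 0.95 | 0.99 |
| 0.5 | 1.06 SD (f = 0.25) | plateau | 0.95 | 0.99 |
| 0.5 | 0.8 SD | linear | 0.56 | 0.70 |
| 0.5 | 0.8 SD | plateau | 0.72 | 0.88 |
| 0.5 | 0.8 SD | late | 0.72 | 0.75 |
| 0.3 | 0.8 SD | linear | 0.39 | 0.62 |
| 0.7 | 0.8 SD | linear | 0.83 | 0.88 |
| 0.7 | 0.8 SD | late | 0.94 | 0.94 |
| 0.85 | 0.5 SD | linear | 0.71 | 0.72 |
| 0.85 | 0.5 SD | plateau | 0.85 | 0.87 |
| 0.85 | 0.5 SD | late | 0.85 | 0.84 |

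The 0.8 and 0.5 SD effects are illustrations, not plan figures. At 0.8 SD and r = 0.5 the between-group F has power 0.24 (linear) or 0.45 (plateau). With no effect, all tests rejected in 1.2% to 1.4% of trials. With all 74 complete, r = 0.5 and 0.8 SD, the interaction has 0.72 (linear) or 0.87 (plateau) and the joint test 0.86 or 0.97.

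The loss for a late effect at high r arises because the joint test has 52 denominator df against 108 for the interaction.

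**If baseline was affected by known allocation.** Suppose one arm's baseline shifts by 0.2 SD (assumed), with no treatment effect and r = 0.5.
- Shift at baseline only: bias is −0.20 for change, −0.20 × 0.5 = −0.10 adjusted, and 0 for the later score alone.
- Shift that persists at all visits: 0 for change, 0.20 − 0.10 = +0.10 adjusted, and +0.20 for the later score alone.

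No one analysis is safest in both cases.

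**The case against.** The strongest reply is that this is a preference about efficiency. The interaction test is valid in a randomised trial, it meets the stated 0.95 at the plan's own inputs when r = 0.5, and adjustment then adds only 0.04. The larger gains need an effect smaller than the plan assumes and a moderate correlation, while the only repeat-measure figure in the document is .85, where the gain nearly vanishes. All of this stands. It limits the size of the point without removing it: that .85 was not obtained in this population, and f = 0.25 implies an end effect above 1 SD, so a smaller true effect is a fair case to plan for.

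A second reply is that the document is written largely in the past tense and reports in-study reliabilities, so data may already exist and a test can no longer be chosen blind. That stands as a condition on the fix.

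A reader might infer more than the documents support:
- That baseline is left unused. On the three-level reading the interaction does use it, through change.
- That adjustment improves every comparison at no cost. It does not for a purely late effect at r of about 0.7 or more.
- That dropout biases the ANOVA. The plan expects losses ("an attrition rate of 30% and a non-attendance rate of 30% (excluding dropouts) were estimated (18"), but bias in completers would need dropout to depend on scores differently by arm. Nothing in the documents shows that, and they say missing data were handled without saying how.
- That the between-group F was the intended test. The sample size rules out that F as its basis, and the text does not say which test was meant.

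**Conclusion.** The point holds as one of efficiency and clarity, not validity. On the natural reading baseline is an outcome level and the treatment test is undefined. The size of the gain rests on the assumed r and on the effect pattern. It is small at the plan's own f (0.95 to 0.99) and material for a smaller effect at moderate r (0.56 to 0.70, or 0.72 to 0.88). At r = 0.85 it is about +0.01 to +0.02, or about −0.02 for a purely late effect. Naming the test is worthwhile whatever r is, because the between-group F loses far more than the choice between change and adjustment. The change is worth making, but the trial's conclusions would not be unsound without it.

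**What to change.** For each of the four outcomes, make the main analysis a linear mixed model of the week-2 and end-of-treatment scores, on all randomised patients by assigned arm. Include baseline as covariate, group, time and group-by-time, with an unstructured covariance. Name the joint group effect over both visits as the single treatment test at 0.0125. Report the end-of-treatment difference with its confidence interval. Keep the group-by-time interaction from the repeated-measures ANOVA as a sensitivity analysis.

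First confirm that baseline was recorded before patients knew their allocation, and so before the foundation course. If it was not, report the adjusted, change-based and unadjusted later-score comparisons together and state the limitation, since which is least biased depends on whether the baseline shift persists.

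If outcome data have already been seen, label the change post hoc.

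The cost is revised wording and modest analysis work in SPSS 25, with no new data. The statistical price is a power loss of up to about 0.02 for a purely late effect at high r.
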